### **Compliance disclaimer**

The clinical trial will be conducted in compliance with the protocol, standard operating procedures, Good Clinical Practice (CPMIP/ICH-135/95) and applicable regulatory requirements.

## Study protocol

# The impact of a moderate calorie and protein restriction program (CARE-PRO) as an efficient and therapeutic strategy in patients with Barrett's Esophagus.

### ABSTRACT

**Introduction:** The increasing incidence of Esophageal Adenocarcinoma (EAC) in several Western countries can be primarily ascribed to risk factors such as obesity, chronic gastroesophageal reflux, dietary habits and alcohol intake. Nevertheless, Barrett's Esophagus (BE), the precancerous lesion, remains the main risk factor for EAC. Several studies supports the role played by the gut microbiota on the modulation of metabolic and immunological pathways. An abnormal state of the microbial ecosystem seems to be involved in the promotion and onset of various diseases, including cancer. In 2009, Yang et al. identified two types of *in situ* esophageal microbiota (type I and II). Type I microbiota was associated with the normal esophageal mucosa and type II microbiota was associated with unhealthy conditions of the esophageal mucosa typical of patients affected by GERD-related esophagitis and BE. Recent studies have shown that diet and lifestyle have an important modulatory role as protective or risk factors for oncological diseases. The World Cancer Research Fund (WCRF) and the American Institute for Cancer Research(AICR) released a review of the evidence that emerged from published studies in the field of nutrition and cancer prevention and summarized their findings into 10 recommendations that everyone should practice to prevent cancer. The concordance between adherence to such indications and risk of onset of various types of cancer (including cancer of the esophagus) has been demonstrated in a recent large prospective study. Several studies have also shown that a moderate caloric and/or protein restriction seems to be able to reduce the risk of neoplastic disease development. The primary aim of this study is to evaluate the impact of a lifestyle-oriented intervention on body weight, waist circumference, biomarkers associated with cancer risk, esophageal microbiota composition and adherence to cancer prevention recommendations after 24 months in overweight or obese BE patients.

**Methods and analysis:** Patients are randomly divided into two arms, a control arm (CA) and an interventional arm (IA). The CA receives information about a correct lifestyle to prevent cancer. The IA is involved in the two-year program of moderate caloric and protein restriction.

At the time of enrollment, anthropometric and body composition measurements will be recorded for each patient and they will be allocated by a data manager in the IA or CA. Blood samples will be obtained from each patient and blood glucose will be determined. Serum metabolic biomarkers will be measured in each serum sample and total proteins will be extracted from fresh frozen esophageal biopsy and will be analyzed to evaluate the insulin signal pathway.

To assess esophageal microbiota profiling, total gDNA will be extracted from matched fresh frozen biopsy. In order to determine a score of adherence to cancer prevention recommendations, participants will be asked to complete a self-administrated questionnaire reflecting WCRF/AICR recommendations. Measurements will occur also at the end point, after two years from the enrollment.

**Ethics and dissemination:** Ethical approval for the study has been received from the Ethics Committee for Clinical Experimentation (Comitato Etico per la Sperimentazione Clinica – CESC) of the Veneto Institute of Oncology (approval number CESC IOV2015/68). This randomised controlled trial will generate substantial information regarding the effect of multimodal approach to reduce

risk of esophageal adenocarcinoma in high-risk population. The results of the study will be disseminated through publication, reports and conference presentation.

## INTRODUCTION

Despite the general improvement in living conditions in recent decades and the increased (average) median age of population, the incidence of certain diseases is increasing, especially those associated with aging. Obesity, central adiposity, type two diabetes (TD2) and insulin resistance are widespread in Western countries, and their role as a risk factor for oncological diseases is well documented.[1–3]

Among malignant cancers, Esophageal Adenocarcinoma (EAC) is steadily becoming the most common esophageal malignancy in several Western countries,[4]. The increasing incidence of this tumor can be primarily ascribed to well-known risk factors such as obesity and chronic gastroesophageal reflux,[5,6] but other lifestyle aspects, such as dietary habits and alcohol intake, are likely involved in the onset of EAC.[6–10]

Nevertheless, Barrett's Esophagus (BE) remains the main risk factor for EAC. BE is a precancerous lesion characterized by replacement of normal squamous epithelium lining the esophageal lumen with columnar-lined metaplastic epithelium. The metaplasia is mainly due to chronic reflux, commonly known as gastroesophageal reflux disease (GERD) and it is endoscopically identified in 5–15% of patients with GERD[11]. BE patients have a 30 to 125 fold greater risk to develop EAC compared with non-GERD population,[12] with a EAC risk of 0.1-0.5% *per year*.[13–15]

Despite the low rate for EAC development in BE patients, its mortality rate after 5 years from diagnosis is higher than 80% and it can be dramatically improved when cancer is diagnosed at an early stage.[16]

Nowadays, BE patients are usually enrolled in expensive endoscopic follow-up programs for early diagnosis. These programs are based on endoscopic biopsy standard protocols and/or random sampling (four quadrant biopsies taken at the gastroesophageal junction and 2 cm above it) and are of dubious effectiveness.[17–21]

Thus, other factors and approaches need to be considered in a strategy to reduce EAC risk.

Several data suggest that obesity, particularly central obesity, could play a causative role in the development of BE and its progression to EAC.[22]

Overweight and obesity are associated with a metabolic dysregulation which is part of the Metabolic Syndrome (MS).[23] MS is associated with a chronic pro-inflammatory state strictly related to an excessive amount of visceral adipose tissue. Abdominal obesity leads to alteration of the normal physiological balance of adipokines with an increase in pro-inflammatory adipokines secretion, such as leptin, and a reduction in anti-inflammatory adipokines, such as adiponectin.[24–26] Central obesity is associated with insulin-resistance, defined as a condition in which target tissues of insulin (liver, adipose tissue and skeletal muscle) have a lower sensibility to insulin action. For this reason, the pancreas produces much more insulin to maintain normal glucose levels in the blood. Chronic hyperinsulinemia, as well as an increased level of serum leptin and a reduced adiponectin secretion, are factors that could play a role in oncogenesis.[27–31]

Moreover, a growing body of evidence supports the role played by the gut microbiota on the modulation of several metabolic and immunological pathways. Gut microbiota is composed of several microbial communities with almost  $10^{14}$  microorganisms.[32,33] An abnormal state of the microbial ecosystem in a host, defined "dysbiosis", seems to be involved in the promotion and onset of various diseases, including cancer.[34,35] The mechanisms by which bacteria can induce carcinogenesis include chronic inflammation, immuno-suppression and immuno-evasion.[35,36] Like the intestinal tract, even the esophagus is colonized by human microbiota (HM). In 2009, Yang et al.[37] identified two types of *in situ* esophageal microbiota (type I and II). Type I microbiota was associated with the normal esophageal mucosa and is characterized by prevalence (about 80%) of Gram-positive taxa belonging to Firmicutes phylum (in particular *Streptococcus* and *Gemella* genera) and low percentages of Gram-negative taxa belonging to Proteobacteria (*Haemophilus* and commensal *Neisseria* genera), Bacteroidetes (*Prevotella* genus) and Firmicutes (*Veillonella* genus) phyla. The type II microbiota was associated with unhealthy conditions of the esophageal mucosa typical of patients affected by GERD-related esophagitis and BE. Type II microbiota is characterized by high presence (more than 50%) of Gram-negative bacteria. The more abundant genera in the type II microbiota included *Veillonella* (phylum Firmicutes), *Prevotella* (phylum Bacteroidetes), *Haemophylus*, *Neisseria* and *Campylobacter* (belonging to Proteobacteria phylum), *Fusobacterium* (*Fusobacteriaphylum*), *Rothia* and *Actinomyces* (belonging to Actinobacteria phylum).[32,33,37]

Recent studies have shown that diet and lifestyle in general have an important modulatory role as protective or risk factors for oncological diseases. In 2007, the World Cancer Research Fund (WCRF) and the American Institute for Cancer Research (AICR) released a wide review of the evidence that emerged from published studies in the field of lifestyle, including physical activity, nutrition and cancer prevention.[38] WCRF/AICR summarized their findings into 10 recommendations that everyone should practice to prevent cancer. Eight out of ten are addressed to cancer primary prevention in the general population and two recommendations are appropriate for "special persons", such as mothers who breastfeed their children and cancer survivors.

The concordance between adherence to such indications and risk of onset of various types of cancer (including cancer of the esophagus) has been demonstrated in a recent large prospective study by Romaguera D., et al.[39]

Several studies have also shown that a moderate caloric and/or protein restriction seems to be able to reduce the risk of neoplastic disease development by bringing back the altered metabolic-hormonal status to a physiological condition and stimulating cell autophagy.[40–45]

Numerous studies have also shown that the effectiveness of a nutritional intervention is greatly improved when the informants, besides providing information, also use health coaching techniques, giving people the opportunity to practice and share acquired knowledge, for example by attending cooking classes, sharing meals and practicing physical activity.[46–58]

## OBJECTIVES

In this study, patients are randomly divided into two arms, a control arm and an interventional arm. The aim of this two-arms randomized clinical trial is to assess the effect of a moderate CALoric-protein REstriction PROgram (CARE-PRO) on metabolic-hormonal condition (such as excessive BMI and/or waist circumference (WC), insulin resistance, unbalanced esophageal microbiota composition, chronic inflammation and adipose tissue-related hormones release) which can represent, when altered, a risk factor for the development of esophageal adenocarcinoma in patients with Barrett's esophagus. The control arm receives information about a correct lifestyle

and suggestions to increase the consumption of fiber and vegetable proteins. The interventional arm instead is involved in the two-year program of moderate caloric and protein restriction.

*-Overall aim of the study*

The main objective of the study is to evaluate the impact of a lifestyle-oriented (diet, physical activity, behavior change) intervention on body weight, waist circumference, biomarkers associated with cancer risk, esophageal microbiota composition and adherence to cancer prevention recommendations (WCRF/ARICR 2007) after 24 months in overweight or obese ( $BMI \geq 25.0 \text{ Kg/m}^2$ ) BE patients.

*-Primary aim*

To examine the effect of a dietary and exercise intervention on body weight and waist circumference reduction in overweight or obese BE patients.

*-Secondary aims*

To assess the impact of CARE-PRO intervention on the relationship between anthropometric parameters (body weight, BMI and WC), metabolic serum biomarkers, the expression of proteins involved on insulin and IGF1 receptors signal transduction and esophageal microbiota composition associated with an increased risk of developing EAC.

- i) To assess the impact of CARE-PRO intervention on the adherence to WCRF/AICR recommendations for cancer prevention.[6,38] Adherence to cancer prevention recommendations will be assessed by a validated score of adherence.[39]
- ii) To evaluate possible differences on CARE-PRO outcomes between elderly ( $> 65$  years) BE patients and younger BE patients ( $<65$  years).
- iii) To evaluate economic costs of the intervention.

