### *-Sample size*

The sample size is based on the primary outcome of a clinically significant change in body weight at the end of the study. A 7% weight loss has been shown to be clinically effective in reducing the risk of diabetes. According to previous data,[44] it is expected that around 30% of patients enrolled in the IA and 15% of those enrolled in the CA will achieve the aforementioned weight loss within the time allotted for trial. In order to reveal a statistically significant difference in the rates of achievement of a 7% weight loss between IA and CA, at least 95 patients are required for each group (power: 80%, type-1 error: 5%). In order to achieve this sample size, we estimate that a pool of 340 patients will be required for recruitment, to allow a recruitment rate of 70% (n=238), and a subsequent drop-out rate of 20% (n=190).

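### The primary aim covers weight and waist, but only the 7% weight-loss rate is named and powered as primary, and no rule says whether success on waist alone counts

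*Combined protocol and SAP*

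**What the plan says.** **Objectives, Primary aim.** "To examine the effect of a dietary and exercise intervention on body weight and waist circumference reduction in overweight or obese BE patients". Two variables are joined by a plain conjunction, and the sentence gives no metric, threshold, time point or order of priority.

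**Objectives, Overall aim.** A wider objective begins "The main objective of the study is to evaluate the impact of a lifestyle-oriented (diet, physical activity, behavior change) intervention on body weight" and goes on to waist, biomarkers, microbiota and adherence at 24 months. The Abstract gives that same wide list the other label: "The primary aim of this study is to evaluate the impact of a lifestyle-oriented intervention on body weight, waist circumference, biomarkers associated with cancer risk".

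**Sample size.** "The sample size is based on the primary outcome of a clinically significant change in body weight at the end of the study". The calculation looks for a "statistically significant difference in the rates of achievement of a 7% weight loss between IA and CA", with 30% expected in the intervention arm (IA) and 15% in the control arm (CA), 95 patients per group, 80% power and 5% type-1 error. Waist does not appear.

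**Trial design.** The intervention lasts 24 months. Blinding of the study team runs until a single primary outcome analysis is complete; that analysis is not described. The principal investigator, study administrator and dietitian are not blinded.

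**Statistical analysis.** Tests are assigned by type of variable or comparison: Fisher's exact for categorical variables, Mann-Whitney between arms, paired t within patients, Spearman for correlation. All are two-tailed and judged at 0.05. The section mentions neither the primary outcome, nor weight, nor waist, nor the 7% threshold, and has no rule for combining tests.

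**The concern.** The 5% type-1 error in the Sample size section describes one comparison. The primary aim allows at least two. Nothing in the plan would be breached if the 7% rate missed significance and the trial then reported its primary aim as met on waist. The same goes, less plainly, for numerical weight change, because the aim speaks of weight reduction and the analysis section has a test ready for numerical variables.

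Two things are at stake. With no true effect, the chance of a false primary claim exceeds the stated 5% if alternative routes count. With a true effect, the verdict can depend on which weight analysis is called primary. Waist is also not a trivial extra in this protocol, which says: "Several data suggest that obesity, particularly central obesity, could play a causative role in the development of BE and its progression to EAC". A reader could therefore treat a waist result as a primary success in good faith.

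**Working it through.** **Inputs.** From Sample size: 30% v 15%, 95 per arm, 80% power, 5% type-1 error. From Statistical analysis: two-tailed tests at 0.05, Fisher for categorical and Mann-Whitney for between-arm numerical comparisons. Assumed, because the documents give none: the distribution of weight and waist change, and their correlation (0.5 to 0.9).

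**1. The plan's own figure.** Pooled formula: n = [z(1-alpha)·√(2·p̄·q̄) + z(0.80)·√(p1·q1 + p2·q2)]² / (p1 - p2)², with p̄ = 0.225.
- √(2 × 0.225 × 0.775) = 0.5906; √(0.21 + 0.1275) = 0.5809; (0.15)² = 0.0225.
- One-sided 5%: (1.645 × 0.5906 + 0.842 × 0.5809)² / 0.0225 = 94.8, so 95. This reproduces the plan.
- Two-sided 5%: (1.960 × 0.5906 + 0.842 × 0.5809)² / 0.0225 = 120.5, so 121.

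The powered quantity is therefore the 7% rate and nothing else. The 95 matches only a one-sided test, which is a separate point and matters here only for the power quoted below.

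**2. Fisher on the 7% rate, 95 per arm, two-sided, by full enumeration.**
- Power at 30% v 15%: 64.9%.
- True size: 3.2% if both arms have 15% responders, 3.4% if both have 22.5%.

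**3. Chance of a false primary claim with no effect on weight or waist.** Simulated normal weight and waist change, responder rate 15% or 22.5%, 100,000 runs per setting.

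| Rule for primary success | Correlation 0.5 | 0.7 | 0.9 |
|---|---|---|---|
| Fisher on rate, or Mann-Whitney on waist | 7.8-7.9% | 7.6-7.7% | 7.3-7.5% |
| Either of those, or Mann-Whitney on weight change | 11.0-11.2% | 10.2-10.5% | 9.0-9.3% |

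- Fisher on the rate, or Mann-Whitney on weight change (waist ignored): 7.0-7.3%.
- Both Fisher on the rate and Mann-Whitney on waist required: 0.4-1.1% across these correlations. If the weight effect is real and waist is null, both succeed in 2.6-3.0%. Since each test is at 5%, the both-must-succeed rule cannot exceed 5%.

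For reference, two independent tests each of exact size 5% would give 1 - 0.95² = 9.75%. The first row is lower because Fisher is conservative and the outcomes are correlated.

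**4. Does the choice of weight analysis matter when the programme works?** Each shape below was set to give 30% v 15% responders (40,000 runs). For the normal shift, z(0.85) - z(0.70) = 1.036 - 0.524 = 0.51 SD.

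| Assumed shape of the effect | Mann-Whitney power | One test significant, the other not |
|---|---|---|
| Normal, all patients shift 0.51 SD | 92.9% | 29.4% |
| Heavy-tailed (t, 3 df), all shift | 94.8% | 30.6% |
| Subset of IA shifts 1, 1.5 or 2 SD | 80.3%, 68.0%, 60.1% | 23.7%, 23.0%, 23.8% |
| 17.6% of IA moved into the responder tail | 43.6% | 30.0% |

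Fisher's power is about 65% throughout. Part of the disagreement comes from that low power: at 131 per arm, where Fisher reaches 80%, it falls to 16-20% for the normal and subset shapes and stays near 29-30% only for the tail shape.

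**5. Waist.** No difference or SD is given, so power for waist, alone or jointly, cannot be derived from the documents.

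**The case against.** The best defence is that an aim is not an outcome. The Sample size section uses the singular, names body weight, sets 7% as the threshold, compares rates between arms and places the comparison at the end of the study; Trial design makes that 24 months and speaks of one primary analysis. A 7% responder is a categorical variable, and categorical variables go to Fisher. A protocol need not list everything that is not primary. Most of this stands. A reader might infer that the trial has no primary outcome or no primary test, and the documents do not support that: both can be worked out.

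The defence does not reach waist. The Primary aim names it, the Sample size section is silent on it, and no inference from the other sections tells a reader whether a waist result alone would count.

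Three further limits are fair. First, the 9-11% figure needs a rule under which any of three tests suffices, and nobody wrote that rule; a reader might take it as the trial's actual error rate, but it is only what the silence would permit. It also leaves out the within-patient paired t test, so it is not a ceiling. Second, the disagreement in step 4 might be read as the two tests pointing in opposite directions. It means only that one reaches significance and the other does not. Third, a reader might take the Abstract's list to mean five primary domains. It matches the Overall aim in Objectives, and Objectives already places biomarkers, signalling proteins, microbiota and adherence under secondary aims, so this is a mislabel.

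**Conclusion.** The point holds, and it concerns waist above all. The primary aim and the primary outcome do not match, and no success rule connects them.

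If success on the 7% rate or on waist suffices, the false-claim probability is about 7-8% rather than 5%; adding numerical weight change as a third route takes it to about 9-11%. If both must succeed, there is no inflation, and the cost falls on power instead. These figures rest on 95 per arm, normal outcomes and correlations of 0.5-0.9, all but the first assumed. The finding that the two weight analyses differ in significance in about 23-31% of trials depends on the assumed shape and is partly a result of low power at 95 per arm.

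The inflation is moderate. It still needs correcting because the success criterion for the primary aim cannot be settled credibly once results by arm are known, and settling it beforehand takes only text.

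**What to change.** **Preferred change.** In Objectives and Statistical analysis, name one primary outcome: the proportion of patients with at least 7% loss of baseline weight at 24 months, compared between IA and CA with two-sided Fisher's exact test at 5%. Make change in waist from baseline to 24 months (Mann-Whitney) the first secondary outcome, tested at 5% only if the primary test succeeds. Make numerical weight change secondary.

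**If the sponsor wants waist to remain primary.** Objectives, Sample size and Statistical analysis must all state two co-primary outcomes and one rule that holds 5%: both must succeed, or a split-alpha or Holm procedure.
- Both must succeed: joint power is below 64.9%. Under assumed waist shifts of 0.51, 0.38 and 0.26 SD it is 62-64%, 52-56% and 31-35%.
- Equal split (0.025 each, two-sided): Fisher on the rate has 54.0% power at 95 per arm.

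**Also.** In Sample size, restate the power for the named test: 64.9% at 95 per arm with two-sided Fisher, not 80%. Whether to enlarge the trial belongs to the separate one-sided versus two-sided point. In the Abstract, relabel the primary aim as the overall aim.

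**Cost.** No new data are needed for the designation itself. Under the preferred change, waist loses primary status and goes formally untested whenever the primary test fails: 1 - 0.649, or about 35% of the time even under the plan's own 30% v 15%. Enrolment began in 2015, so this must be a dated amendment. Because some staff are unblinded throughout, the safeguard should be that nobody deciding the change has seen outcome data by arm.

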## **METHODS AND ANALYSIS**

### **Study design**

*-Study population: inclusion and exclusion criteria*

Patients will be recruited from those included in the Barrett Esophagus and esophageal Adenocarcinoma Risk (EBRA – Esofago di Barrett e Rischio di Adenocarcinoma) Register.

